2.2. Outcome Measures

Fluid biomarker levels in blood and saliva including neuronal damage and immune markers.²³

Visual function tests such as visual field, visual acuity, colour vision, contrast acuity, pupil reactivity, focussing mechanism and eye movements.^{17,18,24,25}

Mental health and quality of life outcomes: social and occupational functioning assessment scale (SOFAS) and self-reported measures such as BIVSS (visual impairments)²⁴, PHQ-9 (Patient Health Questionnaire; depression)²⁶, GAD-7 (General Anxiety Disorder)²⁷, PCL-5 (PTSD checklist for DMS-5)²⁸, SBQ-R (Suicidal Behaviour Questionnaire Revised)²⁸, AUDIT (Alcohol Use Disorders Identification Test)³⁰ and EQ5D5L³¹ (quality of life).

Study name:	Traumatic brain inju	aumatic brain injury related changes in military veterans						
Protocol version number:	3.0	version date:	11 October 2023	Page:	9 of 22			

3. Trial Design and Setting

3.1. Study Design

Prospective observational pilot study

3.2. Study Setting

The study is conducted at the Queen Elizabeth Hospital, Birmingham.

4. Eligibility

4.1. Inclusion Criteria for acute TBI group

- 1. Over the age of 18
- 2. Must have 2 eyes

3. Not all participants will have capacity to consent (e.g. moderate to severe TBI). For these participants, they will require a personal or nominated consultee.

- 4. Willing and able or consented by consultees to follow the protocol
- 5. Moderate or severe head injury requiring admission to the Queen Elizabeth Hospital within the prior 14 days

4.2. Inclusion Criteria for veterans' group

- 1. Over the age of 18
- 2. Must have 2 eyes
- 3. Capacity to consent
- 4. Willing and able to follow the protocol

5. Moderate or severe head injury requiring admission to a military hospital facility or service personnel with planned departure from the Armed Forces within 6 months.

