(4) [name]	Professor of Psychiatry and Youth Mental Health
University of Birmingham Birmingham	[contact]
(5) [name]	Chief Scientific Officer
Bravo Victor	[contact]

Study name:	Traumatic brain injury related changes in military veterans				
Protocol version number:	3.0	version date:	11 October 2023	Page:	3 of 22

STUDY SUMMARY

Title

Traumatic brain injury related changes in military veterans

Study Design

Prospective observational pilot study

Objectives

- To evaluate candidate biomarkers in blood and saliva from veterans and non-veterans with traumatic brain injury and correlate these with visual and mental health assessments and patient reported outcome measures.
- To assess mental health status in traumatic brain injured patients and correlate these with changes in patient reported outcomes to assess quality of life over time.
- To relate these changes after traumatic brain injury to understand how quality of life is affected by injury.

Participant Population and Sample Size

Up to 90 subjects

Outcome Measures

- Fluid biomarker levels in blood and saliva including neuronal damage and immune markers.
- Visual function tests including optical coherence tomography, visual field, visual acuity, colour vision, contrast acuity, pupil reactivity, focussing mechanism and eye movement.
- Mental health and quality of life outcomes: social and occupational functioning assessment scale (SOFAS) and self-reported measures such as BIVSS (visual impairments), PHQ-9 (Patient Health Questionnaire; depression), GAD-7 (General Anxiety Disorder), PCL-5 (PTSD checklist for DMS-5), SBQ-R (Suicidal Behaviour Questionnaire Revised), AUDIT (Alcohol Use Disorders Identification Test) and EQ5D5L36 (quality of life).

Key Eligibility Criteria

Inpatient or outpatient care after moderate to severe traumatic brain injury

Intervention

None

Trial Schema

Study name:	Traumatic brain injury related changes in military veterans				
Protocol version number:	3.0	version date:	11 October 2023	Page:	4 of 22

Study name:	Traumatic brain inju	Traumatic brain injury related changes in military veterans					
Protocol version number:	3.0	version date:	11 October 2023	Page:	5 of 22		

TABLE OF CONTENTS

Protocol development and sign off1	
Protocol Contributors	
Name: 1	
[name]	
[name] 1	
[name] 1	
Protocol Amendments	
Amendment number1	
Date of amendment	
Protocol version number	
Type of amendment1	
Summary of amendment1	
CI Signature Page	
Study Name:	

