1.2. Study Rationale

1.2.1. Justification for participant population

Military personnel are increasingly at risk of TBI during conflicts and especially exposure to blast. Severe TBI is easy to spot but over 80% of TBIs in military personnel are mild TBI (mTBI), which is characterised by short-term loss of consciousness and or altered mental state. Mild TBI has emerged as a signature injury and an important concern in both US and UK military populations, because of the potential for long term negative sequalae. Of military personnel returning from Iraq and/or Afghanistan, up to 40% of military personnel in the US had a mTBI¹⁹, whilst the prevalence in the UK cohort was smaller at around 5%²⁰ with one report suggesting that neuropsychiatric problems could affect as much as 70% of veterans²¹. However, all severities of TBI are associated with a broad range of subsequent psychiatric and neurological disorders including headache, fatigue, sleep disorder, dizziness, amnesia, information processing slowing, executive dysfunction, depression, anxiety and suicidal behaviour²². TBI sustained in combat is also accompanied by posttraumatic stress disorder (PTSD) and bodily trauma, which adds to the difficulty in determination of the relative contribution of each of these factors to eventual outcomes. Biomarkers have the potential to help identify those at risk of poor recovery which would aid deployment of early interventions.

The aim of this investigation is to evaluate candidate fluid biomarkers in blood and saliva from veterans who have suffered a TBI and correlate these with visual assessments, standard clinical assessments of mental health and patient reported outcome measures (PROMs) that assess mental health and quality of life over time. All of the data will be combined to develop a multifaceted algorithm to predict prognosis in veterans and provide pilot data to inform a larger study. The study will also identify biomarkers that can enable rapid decisions as to whether further intervention is required to prevent significant changes to qualify of life in veterans with a TBI and inform rehabilitation strategies to increase optimal management opportunities.

Study name:	Traumatic brain inju	raumatic brain injury related changes in military veterans					
Protocol version number:	3.0	version date:	11 October 2023	Page:	8 of 22		

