1.2.2. Justification for design

This is a prospective observational pilot study. Following 3 groups of participants, including an acute TBI group, a veterans' group with diagnosed TBI and a control group with no previous episodes of brain injury allows us to: (a) assess the changes in fluid and imaging biomarkers and (b) assess mental health status and quality of life over time. Values obtained from levels of biomarkers and measures for mental health status and quality of life will be subtracted from data in the acute TBI and the veteran group. This will reveal changes over time in acute TBI patients who have suffered a TBI and in veterans with TBI. Comparisons between the acute TBI group and the veteran group will then reveal differences between these two groups and whether one group is more susceptible to worse mental health and quality of life status. Since, we will collect longitudinal data, we may be able to tell how long after a TBI do the reported mental health and quality of life problems occur in acute TBI and veterans with a view to developing therapeutic intervention to delay or treat these problems.

We will compare these with the same biomarkers and assessments in control patients (without any episodes of brain injury). This will help us to understand if there is anything different in TBI patients that may tell us who is likely to go onto to develop mental health problems and poorer quality of life outcomes.

Whilst we will aim to perform all investigations at all time points on all patients, not all patients will be able to devote sufficient time and effort to participate and, as this is an exploratory study, we will not exclude patients where they fail to complete all stages of the assessment.

2. Aims, Objectives and Outcome Measures

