4.3. Inclusion Criteria for control group

- 1. Over the age of 18
- 2. Must have 2 eyes
- 3. Capacity to consent
- 4. Willing and able to follow the protocol
- 5. No prior history of head injury (including mild, moderate or severe traumatic brain injury).

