4.4. Exclusion Criteria for all 3 groups

- 1. Patients under 18 years old.
- 2. Patients registered as sight-impaired or severely sight-impaired
- 3. Any known prior pre-existing neuropsychiatric condition: dementia, epilepsy on neuro-epileptic drugs, Parkinson's disease, hereditary neurodegenerative conditions.
- 4. Any known retinal or optic nerve disorder of either eye.
- 5. Pregnancy

4.5. Additional Exclusion Criteria for control group only:

1. Patients have not suffered a TBI or head injury.

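### As worded, veterans' criterion 4.2(5) admits service leavers with no head injury, and control exclusion 4.5(1) contradicts control inclusion 4.3(5)

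*Protocol*

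**What the plan says.** **Veterans.** Protocol section 4.2, item 5, asks for a moderate or severe head injury "requiring admission to a military hospital facility or service personnel with planned departure from the Armed Forces within 6 months". Items 1 to 4 cover age, having two eyes, capacity and willingness. Elsewhere the protocol describes the group by its injury:

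- Section 1.2.2 sets out a veterans' "group with diagnosed TBI and a control group with no previous episodes of brain injury".
- The aim in section 1.2.1 concerns "veterans who have suffered a TBI".
- The study summary gives as key eligibility "Inpatient or outpatient care after moderate to severe traumatic brain injury".
- Section 12.2 describes the subjects of the pilot as patients with TBI, both civilians and veterans.
- Figure 3 schedules a head injury outcome for veterans at close-out. Figure 4 marks the same row as not applicable for controls.

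**Controls.** Section 4.3, item 5, requires "No prior history of head injury (including mild, moderate or severe traumatic brain injury". Section 4.5, headed "Additional Exclusion Criteria for control group only", contains one item: "Patients have not suffered a TBI or head injury".

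**The concern.** TBI exposure is what separates the groups. Section 1.2.2 plans to compare veterans with acute TBI patients, and TBI patients with controls; section 1.2.1 plans a prognostic algorithm for veterans. If the operative eligibility text lets uninjured people into the veterans' group, those comparisons no longer describe TBI in veterans. With a target of 30 per group (section 12.2), a few such people would matter.

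The control wording raises a different problem. A site that enrols the right controls departs from 4.5(1), and a site that follows 4.5(1) departs from 4.3(5).

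**Working it through.** The point rests on reading the criteria together. The protocol gives no figure to reproduce: its only power statement (section 12.2) concerns a within-subject change in retinal nerve fibre layer thickness.

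**Step 1: veterans' criterion.** Let M be a moderate or severe head injury with military hospital admission, and D be service personnel leaving within six months. As punctuated, item 5 is M or D. Take a person with D and no head injury. Item 5 is met through D, and items 1 to 4 do not ask about injury. The shared exclusions in 4.4 (age under 18, sight-impairment registration, listed neuropsychiatric conditions, retinal or optic nerve disorder, pregnancy) do not remove someone for lacking a TBI. That person is eligible.

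The sentence can be read in three ways:

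| Reading | Who enters through the leaver limb |
|---|---|
| Head injury governs both limbs | Only leavers with moderate or severe head injury |
| Leavers are a separate route (literal) | Any leaver, injured or not |
| Leavers are a route for milder TBI | Leavers with TBI of any severity |

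Sections 1.2.1, 1.2.2 and 12.2 rule out the second as the intention. They do not choose between the first and third: 1.2.2 asks only for diagnosed TBI, 1.2.1 puts more than 80% of military TBIs in the mild category, and the summary and 4.2(5) speak of moderate or severe injury.

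**Step 2: control criteria.** Let N be no head injury ever. Section 4.3(5) requires N and section 4.5(1) excludes N. N and not-N has no members, so no one satisfies both.

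**Step 3: veteran versus control.** Let V be the mean difference between injured veterans and controls, in level or in change. Let f be the fraction of the veterans' group without TBI, and assume those people have the same mean as controls. The observed difference is (1-f) x V + f x 0 = (1-f)V. The protocol does not give f; the values below are assumptions.

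| f | People in a group of 30 | Share of V that remains |
|---|---|---|
| 0 (intended reading) | 0 | 1.00 |
| 0.10 | 3 | 0.90 |
| 0.20 | 6 | 0.80 |
| 0.30 | 9 | 0.70 |

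**Step 4: acute versus veteran.** Let A be the acute group's mean difference from controls. The observed contrast is A - (1-f)V = (A - V) + fV. With A and V both positive, it grows by fV if A exceeds V. If V exceeds A, the gap first narrows and can then change sign. The direction is not fixed.

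**Step 5: biomarker-outcome correlation.** In a mixed group the covariance is (1-f)c1 + f c0 + f(1-f) x dx x dy. Here c1 and c0 are the covariances among injured and uninjured people, and dx and dy are the differences between the two in mean biomarker and mean outcome. The last term can raise the correlation or lower it.

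**The case against.** The strongest reply is that both lines are drafting slips whose intention is plain.

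- **Controls.** This largely stands. Sections 1.2.2 and 4.3(5), the consent section (controls are approached after an injury that spares the head) and Figure 4 all point the same way. A reader might infer from 4.5(1) that the reference group has no definition, or that head-injured people would be enrolled as controls. The documents do not support that: the group is described consistently everywhere else, and exclusions are applied after inclusions. What remains is a direct contradiction between two operative criteria.
- **Veterans.** The reply stands in part. The head injury can be read as governing both limbs, and the rest of the protocol expects TBI. The research team also talks to the patient and reviews the notes before confirming suitability. But section 5 adds no TBI requirement to that check, some veterans come forward through advertisements and charities, and the intended severity cannot be recovered from the sentence.

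Three stronger inferences are tempting:

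- **Most of the veterans' group would be uninjured**, since section 1.2.1 puts mild TBI at around 5% of a UK cohort. Recruitment through a rehabilitation centre and veterans' charities makes that figure a poor guide to f, and the protocol offers no other.
- **All veteran comparisons and correlations would be diluted.** Steps 4 and 5 show that the direction is open for two of them.
- **A stated power is lost.** The protocol claims no between-group power, so there is none to reduce.

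**Conclusion.** Both lines are wrong as written. The leaver limb of 4.2(5) carries no head-injury condition, which contradicts the protocol's own description of the group. Section 4.5(1) excludes the very people 4.3(5) requires. Neither conclusion depends on a numerical assumption.

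The practical effect of the control error is small, because the intended rule is evident. The effect of the veterans' error depends on f, which the protocol neither states nor limits. The (1-f) shrinkage of the veteran-versus-control difference further assumes that uninjured leavers resemble controls on average. If they differ because of service-related PTSD or bodily trauma, which section 1.2.1 describes as accompanying combat TBI, the size would differ. For the other two analyses only the presence of bias can be stated, not its direction.

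**What to change.** 1. Amend 4.2(5) so that a documented TBI is required of each veteran participant, with the two service conditions as alternatives beneath that requirement. The sponsor should state the required severity and reconcile it across the study summary and sections 1.2.1, 1.2.2 and 4.2.
2. Delete 4.5(1), since 4.3(5) already covers it, or reword it as an exclusion for any history of TBI or head injury.
3. If personnel without TBI are already enrolled, identify them and analyse them separately from the veterans' TBI group.

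The cost is two lines in an amendment and possibly a narrower pool of eligible service leavers.

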4.3. Inclusion Criteria for control group

- 1. Over the age of 18
- 2. Must have 2 eyes
- 3. Capacity to consent
- 4. Willing and able to follow the protocol
- 5. No prior history of head injury (including mild, moderate or severe traumatic brain injury).

4.4. Exclusion Criteria for all 3 groups

- 1. Patients under 18 years old.
- 2. Patients registered as sight-impaired or severely sight-impaired
- 3. Any known prior pre-existing neuropsychiatric condition: dementia, epilepsy on neuro-epileptic drugs, Parkinson's disease, hereditary neurodegenerative conditions.
- 4. Any known retinal or optic nerve disorder of either eye.
- 5. Pregnancy

4.5. Additional Exclusion Criteria for control group only:

1. Patients have not suffered a TBI or head injury.

4.6. Eligibility criteria for personal consultee

1. Knows the incapacitated person well (i.e. friend or family member)

Study name:	Traumatic brain inju	raumatic brain injury related changes in military veterans					
Protocol version number:	3.0	version date:	11 October 2023	Page:	10 of 22		

- 2. Must not have a financial interest in the project
- 3. Capacity to consent

4.7. Eligibility criteria for nominated consultee

- 1. Only appointed if no family member or friend is willing or able to act as a consultee
- 2. Must have no connection with the project
- 3. Capacity to consent

5. Consent

A member of the clinical care team (e.g. doctor, research nurse or practitioner) at Queen Elizabeth Hospital Birmingham will first identify potential acute TBI and control group participants to ascertain whether they are interested in participating in the study. They will be approached after either head injury for the acute TBI group (i.e. 0-14 days post-injury) or any other injury not involving the head for the control group in the inpatient ward or in clinic (outpatient) or during telephone / virtual follow up.

Veterans will be recruited through existing links with the military and as they are discharged from military care into NHS care. This includes partner site the Defence Medical Rehabilitation Centre in Stanford Hall where the clinical care team will identify suitable participants and obtain full written consent prior to participants visiting the Queen Elizabeth Hospital in Birmingham for blood/saliva collection and all tests. Veteran's will also be recruited through advertisements and direct contact with veterans' charities such as Bravo Victor and Blind Veterans UK.

Once an acute TBI or control patient or a veteran has expressed an interest in participating, and has provided full written consent to the clinical care team, they will be introduced to a member of research team (e.g. post-doctoral research fellows or assistants). A member of the research team will determine by talking to the patient and review of the patient's notes whether or not the patient is suitable to participate in the study. If the patient is not suitable for inclusion in the trial, their data will not be retained.

In addition, veterans who have already been discharged from the military will also be recruited through advertisements and direct contact with veterans' charities such as Bravo Victor and Blind Veterans UK. These patients will contact the research team if interested and a trained member will obtain full written consent prior to determining the suitability of the participant in the study.

For all participants, a full explanation about the study objectives, visits and assessments will be given in detail and a patient information sheet (PIS) will be provided to facilitate this process. Investigator(s) will also stress that participation is voluntary and that the participant is free to refuse to take part and may withdraw from the study at any time.

In the event that the patient is unconscious, a relative or next of kin will be sought out by the clinical care team to read the Personal Consultee information sheet and personal consultee declaration form (PersCDF). If they are happy for the patient to be involved in the study, they will be asked to sign the consultee declaration form and witnessed by one of the clinical care or research team. If, after including the patient by the PersCDF, the patient's family member thinks the patient would no longer want to be included in the study, they will be withdrawn. For unconscious patients or patients who regain consciousness but do not have the ability to consent, only blood will be collected over time and other measures such as collection of saliva, eye imaging test, SOFAS and PROs will not be possible.

If the patient regains consciousness and is able to consent, the consultee would be notified and the patient would be offered a separate regained capacity PIS and asked if they are happy to be in the study and sign the study consent form. If they would not like to be in the study, the information already collected will be retained and they will be withdrawn from the rest of the study.

Study name:	Traumatic brain inju	Fraumatic brain injury related changes in military veterans					
Protocol version number:	3.0	version date:	11 October 2023	Page:	11 of 22		

If the patient has no relative or next of kin available, a member of the patient's clinical care team will be asked to read the study protocol and PIS and nominated consultee declaration form (ProfCDF). If they are happy for the patient to be involved in the study, they will be asked to sign the nominated consultee declaration form.

All potential participants will be offered the opportunity to discuss and ask questions about the research with a member of the research team after they were introduced by the clinical care team. If the participant expresses a desire to participate in the study, they will be asked to sign and date the latest version of the Consent Form prior to any investigations being carried out. A member of the research or clinical care team will then sign and date the form. A copy of the Consent Form will be given to the participant, a copy will be filed in the medical notes, and the original placed in the Investigator Site File (ISF). Once the participant is entered into the study, the participant's unique study identification number will be entered on the Informed Consent Form maintained in the ISF.

Details of the informed consent discussions with the clinical care team will be recorded in the participant's medical notes. This will include date of discussion, the name of the study, summary of discussion, version number of the PIS given to participant and version number of ICF signed and date consent received. Where consent is obtained on the same day that the study related assessments start, a note will be made in the medical notes as to what time the consent was obtained and what time the procedures started.

At each visit the participant's willingness to continue in the study will be ascertained and documented in the medical notes. In the unlikely event that a patient loses capacity while enrolled in the study, a personal consultee or a nominated consultee will be appointed to decide for the patient. If the patient regains consciousness again, the consultee will be notified, and the patient will be given a regained capacity PIS as above. If they would like to stay in the study, they will be asked to sign the consent form. Throughout the study, the participant will have the opportunity to ask questions about the study. Any new information that may be relevant to the participant's continued participation will be provided. Where new information becomes available which may affect the participants' decision to continue, participants and consultees will be given time to consider and reconfirm continuation in the study. The participant's right to withdraw from the study will remain.

